A randomized, unblinded controlled trial was performed in St. John's, among patients without indwelling catheters, using the same intervention.(11) Results of positive urine cultures from 110 consecutive inpatients at two urban acute care hospitals were randomised to standard report or modified report. Specimens randomized to the modified report were reported as follows: “This POSITIVE urine culture may represent asymptomatic bacteriuria or urinary tract

infection. If urinary tract infection is suspected clinically, please call the microbiology laboratory for identification and susceptibility results.”

Exclusion criteria were age less than 18 years, pregnancy, presence of an indwelling urinary catheter, samples from patients already on antibiotics, neutropenia, or admission to an Intensive Care Unit. Patients were followed for seven days, and physician treatment decisions were observed. 76/110 (69%) of positive urine cultures represented ASB. The proportion of appropriate treatment (UTI treated plus ASB not treated) was higher in the modified arm than in the standard arm (44/55 (80.0%) vs 29/55 (52.7%), absolute difference=-27.3%, RR=0.42, p=0.002, Number needed to report for benefit=3.7).

There were two bacteremias in the modified report group, and one bacteremia in the standard report group, none of which were considered related to the intervention. There were two deaths in the modified report group, and one death in the standard report group, none of which were considered related to the intervention. Based on this trial, the intervention was considered safe over 7 days of followup, and effective to reduce inappropriate treatment, but further study would be required among populations excluded from the trial.

We propose to repeat the trial using an identical design and intervention, but including only urine collected from indwelling catheters. The control arm is standard of care. We hypothesize that the modified reporting intervention will also demonstrate effectiveness at reducing treatment of ASB in this population, without causing harm.

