## **Sample size**

In the previous trial of the same intervention, modified reporting increased the appropriateness of treatment from 29/55 (52.7%) to 44/55 (80.0%) ( $p=0.002$ ), for an absolute difference of +23%. Accepting a risk of type 1 error of five percent, and a risk of type 2 error of twenty percent, the study will require  $2N=90$  patients. To account for missing data, recruitment will be increased to 100 patients.

The microbiology laboratory receives 130 urine specimens per day, with 30 percent reported as significant growth (40 specimens per day). Twenty-five percent are submitted from inpatients (10 specimens per day). Approximately 33% of inpatient urines are collected from catheters, however collection method is not always provided to the laboratory. This leaves approximately three urine specimens per day which may be eligible for inclusion. In the previous trial, approximately 40% of eligible specimens were excluded based on exclusion criteria. Recruitment of 100 specimens will require approximately 60-90 days.

The statistical test to be used is a comparison of proportions between two groups (T test, two-sided analysis). Because true diagnosis may be biased by lack of access to clinical information, an intention to treat analysis including all patients randomized will be performed.

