### **Statistical methods**

All specimens randomised and reported will be included in the Intention-to-treat (ITT) analysis. Specimens inappropriately included will be excluded from the Per-protocol (PP) analysis. The proportion of appropriate treatment will be compared using two-sided Pearson chi squared test (SPSS 23.0, IBM, USA). Adjusted analysis will not be performed. A subgroup defined as specimens in which physicians requested complete reporting will be analysed for appropriateness, compared to the standard reporting arm. Missing data will not be imputed.

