### **Data monitoring**

A data monitoring committee will not be used, as a single investigator will assume responsibility for data quality. A single interim analysis at approximately 50% recruitment will be performed, and the study stopped if the primary outcome achieves statistical significance.

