### **Implications**

A reduction in inappropriate antibiotic treatment may reduce complications of treatment such as diarrhea due to *Clostridium difficile*, selection of bacteria towards drug resistance, and cost of treatment. If the intervention is determined to be safe, it may be considered for implementation in routine laboratory practice. The results will generalize to adult inpatients in Canada and around the world.

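### If the trial stops early for efficacy, the observed gain will on average be overstated (about 36 points against a true 27), and the plan specifies neither an estimate nor any allowance for early stopping

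*Combined protocol and SAP*

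**What the plan says.** The Data monitoring section sets a single interim analysis at roughly 50% recruitment, with "the study stopped if the primary outcome achieves statistical significance". It names no interim significance level, boundary or minimum sample.

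The analysis of the primary outcome is in the Statistical methods section: "The proportion of appropriate treatment will be compared using two-sided Pearson chi squared test". That section names no effect measure, confidence interval or correction for early stopping. Neither does any other section.

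The Sample size section sets the errors ("Accepting a risk of type 1 error of five percent, and a risk of type 2 error of twenty percent"), arrives at 90 patients and adds an allowance for missing data ("recruitment will be increased to 100 patients"). Half of 100 is 50 specimens, or about 25 per arm.

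The Background summarises both earlier studies of the intervention by a number needed to report for benefit. The Implications section says of the intervention, provided it is found to be safe, that "it may be considered for implementation in routine laboratory practice".

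**The concern.** A rule that stops the trial when the result is significant acts as a filter on the observed difference. With about 25 per arm only large observed differences pass, so trials that stop early show, on average, more than the true gain.

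What is at stake is the size of the effect that readers take away. The earlier studies were summarised by number needed to report, and the same figure is likely to be quoted here and weighed when routine reporting is considered. The planning rates come from non-catheterised patients. If the true gain in catheterised patients is smaller, the gap between a stopped result and the truth widens.

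This is a different matter from the type 1 error of testing twice. A correction to the interim significance level would not address it.

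**Working it through.** **Inputs.** Standard report p1 = 29/55 = 52.7% and modified report p2 = 44/55 = 80.0% (Sample size). Two-sided Pearson chi-squared test (Statistical methods). Interim at 25 per arm (half of 100, equal allocation). Interim level p<0.05, which is an assumption because the plan names none.

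The Sample size section also prints "for an absolute difference of +23" percent, but its own rates differ by 80.0 − 52.7 = 27.3 points. The Background agrees in size ("absolute difference=-27.3%, RR=0.42, p=0.002"; the negative sign refers to inappropriate treatment).

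**1. Reproduce the plan's 90.** With pooled rate p̄ = 73/110 = 0.664:

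n per arm = [1.96·√(2p̄(1−p̄)) + 0.8416·√(p1(1−p1) + p2(1−p2))]² / (p2−p1)² = [1.310 + 0.538]² / 0.0744 = 45.9, so 46 per arm, 92 in total.

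The unpooled version gives 88. The plan's 90 lies between them. A 23-point difference would need 126 to 136 with the pooled formula, so 90 rests on 27.3 points, and that value is used below.

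**2. What passes the interim test.** Near the pooled rate, significance needs a difference of about 1.96·√(2 × 0.664 × 0.336 / 25) = 0.262. Counts move in steps of 1/25 = 4 points. Exact enumeration gives the smallest significant gain by the number appropriate in the standard arm:

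| Standard arm, of 25 | Smallest significant gain |
|---|---|
| 4 to 15 | 7/25 = 28 points |
| 16 to 18 | 6/25 = 24 points |
| 19 to 20 | 5/25 = 20 points |
| 21 | 4/25 = 16 points |

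**3. Chance of a stop and mean observed gain given a stop.** For each pair of counts (x, y), multiply the two binomial probabilities and keep the pairs with two-sided p<0.05. Then P(stop) is the sum over those pairs, and the mean given a stop is the sum of probability × (y−x)/25, divided by P(stop). Stops in either direction are counted.

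| True gain | P(stop) | Mean gain given a stop | Number needed: apparent / true |
|---|---|---|---|
| 27.3 points | 56.0% | 36.3 | 1/0.363 = 2.8 / 3.7 |
| 15 points | 21% | 33.2 | 1/0.332 = 3.0 / 6.7 |
| 10 points | 13% | 30.5 | 1/0.305 = 3.3 / 10 |

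At a true 27.3 the mean excess is 36.3 − 27.3 = 9.0 points, and 2.9% of stops fall below 27.3. Counting only stops that favour the modified report, the means at 15 and 10 points are 33.6 and 32.8.

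**4. Average over all trials.** Trials that continue to 50 per arm average 21.5 points. Overall: 0.560 × 36.3 + 0.440 × 21.5 = 20.3 + 9.5 = 29.8, an excess of 2.5 points.

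**5. Sensitivity.**
- 22 to 28 per arm: means given a stop of 38.5 down to 35.1.
- 50 specimens under simple randomisation, as planned: P(stop) 54.3%, mean 36.7.
- Interim at half of 90 (23 per arm): mean 37.8.
- Continuity-corrected test: mean 39.0.
- True gain of 23 points: 34.4 to 35.2.

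**6. A stricter boundary.** With z = 2.80 (p<0.0052) and a true 27.3, P(stop) falls to 22% and the mean given a stop rises to 44.3.

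**7. Precision.** The 95% half-width is 1.96·√[(0.249 + 0.160)/n]: 25 points at n = 25 per arm and 18 at n = 50.

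**8. A bias-adjusted estimate.** A Whitehead-type estimate is the true gain whose expected estimate, over all trials, equals the observed gain. For 13/25 against 20/25 it moves 28 to about 25. For 13/25 against 22/25, close to the typical stopped result, it moves 36 to only about 34 (number needed 2.9).

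**The case against.** **Inflation given a stop is common to every efficacy stop, and the bias over all trials is small.** Both are true: the overall excess is 2.5 points. At the planned effect an ordinary 95% interval from a stopped trial would still cover the truth about 93.6% of the time. But readers see the one trial that was run, and the plan does not commit to an interval. At smaller true gains the interval also protects less: 13/25 against 22/25 gives 12.6 to 59.4, which excludes a true gain of 10.

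**The 56% belongs to the planning effect.** This stands. It is borrowed from another population. Where the inflation is greatest, at 10 to 15 points, stops are much rarer.

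**A reader might infer that any stopped trial must show at least 28 points.** The planned test does not support that. If 16 or more of 25 are appropriate in the standard arm, gains of 16 to 24 points are significant.

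**A reader might infer that the plan commits to reporting the raw difference, or rules out a sequential correction by declining adjusted analysis.** The text does neither. It is silent on the estimator, and the remark on adjustment most naturally concerns covariates. The raw difference is the likely default, since the earlier trial is summarised that way.

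**Recruiting on regardless leaves the interim without a purpose.** This is fair. No futility or safety rule is attached to the look, so dropping the efficacy look is an equally good answer.

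**Conclusion.** The point holds as a statement about averages. Under the plan's own rates, 25 per arm and an assumed p<0.05 at the interim, an early stop is somewhat more likely than not, and it carries a mean overstatement of 9.0 points. The direction is stable across the variations tried. The size depends on rates from non-catheterised patients and on an interim level that the plan leaves open.

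Two stronger conclusions are not supported: that every stopped trial overstates the effect, and that a standard bias-adjusted estimate would put it right. That estimate targets the 2.5-point bias over all trials. Given a stop, it leaves about 34 − 27 = 7 of the 9 points in place.

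This is an improvement worth making before the interim data are seen. It does not invalidate the design.

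**What to change.** **Preferred.** Amend the Data monitoring section so that an efficacy result at the interim does not end recruitment, or drop the efficacy look. If a look is kept, state what it is meant to decide. Complete the planned 100 specimens. This removes the selection and brings the half-width from about 25 to about 18 points. The Sample size section expects 60 to 90 days for 100 specimens, so the second half costs about 30 to 45 days of recruitment that is already planned.

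**If the efficacy stop is kept.** Amend the Statistical methods section to:
- report the risk difference with a 95% interval that accounts for the interim look;
- state that an estimate from a trial stopped for efficacy is inflated on average;
- attach the same caveat to any number needed to report.

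A Whitehead-type estimate may be shown beside the raw difference, but it must not be presented as removing the inflation. The cost is a paragraph and a short calculation.

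Either change should be made before the interim. The plan has no data monitoring committee and an unblinded analyst, so a choice made afterwards could be influenced by the result. The downside is a somewhat longer trial or a less favourable reported effect.

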### **Harms**

Serious adverse events will be reported to the ethics committee within 24 hours. Adverse events will be collected by the investigators at day 2 and day 7. Patients with adverse events will be provided care in hospital.

### **Auditing**

There will not be auditing of trial conduct during or after the trial.

### **Research ethics approval**

The protocol will be submitted to the Provincial Health Research Ethics Board.

Physician consent requirement will be requested to be waived because the intervention poses no more than minimal risk to participants. Patient consent requirement will be requested to be waived because physicians were the research subjects. A letter will be sent to all inpatient physicians informing them about the study prior to recruitment, and a debrief meeting, offering an opportunity to withdraw physician participation, will be provided.

The benefit of this study to patients includes a reduction in adverse events caused by inappropriate antibiotic treatment. The risk to patients includes possible untreated CA-UTI. The benefit to physicians includes education toward appropriate treatment of CA-ASB. The risk to physicians includes additional effort to access laboratory results for CA-UTI.

### **Protocol amendments**

Protocol amendments will be submitted to the ethics committee and trial registry and informed to investigators.

### **Consent or assent**

Not applicable.

### **Confidentiality**

Identification of patients will be required during data collection, but will be removed from trial dataset before analysis. No identifiers will be included in reporting of results.

### **Declaration of interests**

The investigators and sponsor hold no financial interests in the trial.

### **Access to data**

The trial dataset and protocol will be accessible to the investigators during the trial, and made publically available after the analysis is completed.

### **Ancillary and post-trial care**

There will be no post-trial care provided.

### **Dissemination policy**

Investigators will communicate trial results via unrestricted publication. All investigators are eligible for authorship, according to contribution.

### **Biological specimens**

There will be no collection, testing or storage of biological specimens for genetic or molecular analysis.

### **Budget**

The only expense of the project will be the graduate student to collect the data, perform the analysis and write the manuscript.

### **Implications**

A reduction in inappropriate antibiotic treatment may reduce complications of treatment such as diarrhea due to *Clostridium difficile*, selection of bacteria towards drug resistance, and cost of treatment. If the intervention is determined to be safe, it may be considered for implementation in routine laboratory practice. The results will generalize to adult inpatients in Canada and around the world.

